Most of the 39 departments offering female incontinence surgeries in Norway use traditional MUS. However, one of the largest hospitals, Akershus University hospital (AHUS), has been using shorter slings as their preferred MUS since 2009, initially SIMS Ajust and later TTVT-A. At AHUS, we therefore have a unique opportunity to study the long-term results and complication rates of shorter slings by inviting women back for a long-term follow-up after undergoing sling surgery at AHUS. In addition to quality of life, complications, and patient satisfaction, this follow-up provides the possibility of investigating sling position using 2D dynamic and 3D transperineal ultrasound (TPUS) (34-37). This innovative technique that dynamically investigates the pelvic floor and sling placement is not widely used in Norway, but is available at AHUS, which also has expertise in advanced ultrasound within the research group. How the positioning of intermediate slings under the urethra may affect long-term success rates and adverse events is largely unknown. Studies on traditional slings suggest that placement more proximal or distal to the mid-part of the urethra is associated with poorer outcomes (34-36).

Whether this is coincidental or represents an actual association between sling position and long-term success and complication rates is not established for intermediate slings. To go even further, we will evaluate if there is an “optimal sling placement zone”, particularly for shorter slings. This information is currently lacking and makes it difficult for gynaecologists evaluating patients in need of repeat surgery, due to either treatment failure or long-term complications. Understanding the biomechanical effects visualized by ultrasound of the increasingly popular shorter slings would be pioneering work and enable researchers and doctors to further develop the treatment techniques for female incontinence.

Research questions and hypotheses, theoretical approach and methodology

PhD-project, Part 2

Our over-all aim is to evaluate long-term subjective and objective outcomes of shorter slings.

Study design: Prospective observational study

1) Long-term subjective outcomes

Study population: Women treated with SIMS Ajust (n = 744) at Akershus University Hospital between 2009 and 2016 and Intermediate sling TTV-A (n= 318) at Akershus University Hospital between 2016 and 2020.

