Follow-up: Potential study participants for both groups will be identified in the local quality database for female incontinence surgery (local NFIR) at AHU S and invited to a long-term follow-up (4-14 years) with questionnaires. The following questionnaires will be sent electronically to the patients together with study invitation and consent form: The validated NFIR questionnaire, the validated Pelvic Floor Impact Questionnaire (PFIQ-7) (38, 39) as well as additional questions regarding pain (40).

- a. *Primary outcomes:* Long-term subjective cure rate.
- Long-term subjective cure is estimated by calculating a stress urinary incontinence index score (SUIS) from 4 clusters of questions measuring degree of symptom bother in the validated NFIR questionnaire, from 0 (no symptoms) to 12 (high symptom load) where a score < 3 is defined as subjective cure (41).
- b. *Secondary outcomes:* Long-term treatment satisfaction scores, quality of life score and complication rates.
- Differences in improvement of quality-of-life using a Quality-of-life index score (QoLIS) generated from 4 questions in the NFIR questionnaire measuring QoL impact. This index ranges from 0 (excellent quality of life) to 16 (poor quality of life) (41). In addition, the Pelvic Floor Impact Questionnaire (PFIQ-7) (38, 39) will be used to further evaluate the Quality-of-life impact.

- Differences in treatment satisfaction rates are defined as the percentage of women answering “very satisfied with treatment” given the options “very satisfied”, “moderately satisfied”, “neither satisfied nor dissatisfied”, “moderately dissatisfied” or “very dissatisfied” in the NFIR questionnaire.
- Differences in total complication rates (all types included), re-operation rates, vaginal tape exposure, persistent and de novo urgency incontinence and prolonged pain.
 - Persistent and de novo urgency incontinence is calculated from the NFIR questionnaire using 4 clusters of questions that generate an urgency urinary incontinence score (UUIS) quantifying the degree of urgency symptom bother from 0 (no symptoms) to 8 (high symptom load) (41). De novo urgency incontinence will be defined as having had a UUIS of ≥ 4 at the long term follow up in women who had no urgency incontinence symptoms before surgery (preoperative urgency urinary incontinence score = 0).

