 - Differences in prolonged pain defined as postoperative pain more than 3 months after surgery in the NFIR questionnaire or having had treatment for pain caused by the surgery, e.g removal of the sling or part of the sling. Patients having persistent ongoing pain will further be asked to answer a newly developed non-validated NFIR pain questionnaire (40).

2) Long-term objective outcomes

[figure not shown]
Study population: The 318 women having been treated with the currently most used shorter sling (TVT-A) at Akershus University Hospital between 2016 and 2020 will be invited to a physical follow-up where they will undergo a clinical examination including assessment of objective cure, sling erosions and development of pelvic organ prolapse using the POP-Q system (42).

Exposure: Having had TVT-A sling operation at AHUS.

- a. *Primary outcomes:* Long-term objective cure rates.
- Objective cure will be defined as having no leakage (0 g) at a cough-jump pad weighing stress test (43).
- b. *Secondary outcomes:* The same as defined under 1) Long-term subjective outcomes.
- In addition, we will evaluate differences in the rate of mesh exposures and the development of pelvic organ prolapse (POP) using the POP-Q evaluation system (42).
- The severity of tape exposure will be evaluated using the ICS and IUGA prosthesis and graft complication classification system (44). In addition, we will evaluate the intervention for surgical complications using the Clavien-Dindo Classification (45, 46).

PhD-project, Part 3

We will study the positioning of the shorter sling TVT-A under the urethra using dynamic 2D and 3D ultrasound. We will evaluate if there is an “optimal sling placement zone” for shorter slings.

Our aim is to study the association between sling position, tension and anchoring under the urethra, and subjective and objective cure rate, and long-term complication rates, especially chronic pelvic pain.

Our null hypothesis is that there are no associations between sling position, tension or anchoring of the tape and subjective and objective outcomes including complications such as chronic pain development.

Study design: Prospective observational study

Study population: 318 women having had surgery with the intermediate sling TVT-A at AHUS between 2016 and 2020.

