Follow-up: Women who consent to study participation and attend the physical follow-up will undergo a clinical examination that includes a transperineal ultrasound (TPUS) examination in the dorsal lithotomy position using a 3,5-6 MHz curved array abdominal probe (47). The TPUS volumes and images will be obtained with an empty bladder at rest and under full Valsalva (48).

Exposure: Position, tension (shape) and anchoring of the sling, and measuring sling position in relation to well-defined anatomical markers.

- a. *Primary outcomes:* Any association between sling position, tension or anchoring and subjective and objective cure rate, complication rates and especially the development of chronic pelvic pain. For the definitions of cure rates, *see under part 2*.
- b. *Secondary outcomes:* Any association between sling position, tension or anchoring and long-term complications, especially chronic pelvic pain, *see part 2*.

Statistics, power and sample size:

PhD-project, Part 2

This is a follow-up study of all women having been operated at AHUS with SIMS Ajust or TTVT-A in the study period. Few studies with long-term outcomes after shorter slings have been published. The first part of the long-term follow-up will therefore be a prospective follow-up study with no group comparisons. For this part, power calculations are not feasible as all women having had SIMS Ajust or TTVT-A in the study period consenting to study participation will be analysed for subjective outcomes, whereas all women in the TTVT-A group consenting to study participation will be analysed for objective outcomes.

PhD-project, Part 3

For the transperineal ultrasound (TPUS) part of the project, various outcomes will be evaluated based on sub urethral sling position, tension and anchoring. As there is little scientific published data on how sling placement affect subjective and objective outcomes of sling surgeries, a pre-study sample size estimation must in part be made on best clinical guess. Based on the following assumptions:

We estimate that 80 % of the women will have the sling placed in the “optimal position” and 20 % outside the optimal position as shown in a small study published in 2017 by Hegde and co-workers (37). Therefore, the estimated group ratio will be 1:4.

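### Re-operation, tape exposure and total complication rates are tied to no time since surgery, although years observed are almost wholly determined by which sling a woman received

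*Protocol*

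**What the plan says.** The study population of Part 2, section 1 (Long-term subjective outcomes) consists of two consecutive cohorts. The first is described as "Women treated with SIMS Ajust (n = 744) at Akershus University Hospital between 2009 and 2016". The second is the 318 women who received TVT-A at the same hospital from 2016 to 2020. Only 2016 is common to both. The follow-up paragraph of that section says that women in both groups are "invited to a long-term follow-up (4-14 years) with questionnaires".

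The secondary outcomes there include "Differences in total complication rates (all types included), re-operation rates, vaginal tape exposure, persistent and de novo urgency incontinence and prolonged pain". For total complications, re-operation and tape exposure, no time point, denominator or person-time is given, and the protocol does not mention collecting event dates. Two neighbouring definitions show how such outcomes are conceived:

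- Satisfaction: "Differences in treatment satisfaction rates are defined as the percentage of women answering" the top category. This is the one place where a rate is defined, and it is a percentage of women.
- Prolonged pain: "postoperative pain more than 3 months after surgery in the NFIR questionnaire or having had treatment for pain caused by the surgery". This is an ever/never item with no upper time limit.

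The statistics section for Part 2 states: "The first part of the long-term follow-up will therefore be a prospective follow-up study with no group comparisons".

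**The concern.** Cure and the urgency score are statuses on the day of follow-up. Re-operation, sling removal and an all-types complication total naturally read as having ever occurred since surgery, so the share of women affected can only grow as observation lengthens. Because the two slings were used in successive calendar periods and are assessed at roughly the same time, the Ajust women have been observed for about twice as long. A crude percentage would therefore reflect operation year as well as sling, and a difference between slings could appear where none exists.

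This bears on the study's purpose. The section on potential impact names evidence on short- and long-term success and on the incidence of severe long-term complications, for informing women. An incidence with no stated period cannot be used for that.

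**Working it through.** **Inputs from the protocol.** Ajust: 744 women, operated 2009-2016. TVT-A: 318 women, operated 2016-2020. Follow-up: 4-14 years.

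**Assumptions (not in the protocol).** Contact in 2023 or 2024, operations spread evenly over the stated years, and the same yearly event risk h for both slings.

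**1. The stated follow-up range.** Years observed = contact year minus operation year.

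| Contact | Ajust | TVT-A |
|---|---|---|
| 2023 | 7-14, mean 10.5 | 3-7, mean 5.0 |
| 2024 | 8-15, mean 11.5 | 4-8, mean 6.0 |

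The upper end (2023 - 2009 = 14) and the lower end (2024 - 2020 = 4) both reproduce, though not from one calendar year. To the nearest year the range fits contact in 2023-2024. The ratio of mean follow-up is 10.5/5.0 = 2.1 or 11.5/6.0 = 1.9.

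**2. Equal constant risk.** Expected share of women with an event = mean over operation years of 1 - exp(-h·t).

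| h per year | Contact 2024: Ajust, TVT-A, ratio | Contact 2023: ratio |
|---|---|---|
| 0.25 % | 2.8 %, 1.5 %, 1.90 | 2.09 |
| 0.5 % | 5.6 %, 3.0 %, 1.89 | 2.07 |
| 1 % | 10.8 %, 5.8 %, 1.86 | 2.04 |

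Holding strictly to 4-14 years and splitting at 2016 (Ajust 7-14, TVT-A 4-7), the ratio is 1.88 at 0.5 % and 1.86 at 1 %. It falls as risk rises, to 1.69 at 5 % per year. Over contact dates from 2023 to 2025, several ways of placing operations within years, and risks of 0.5-5 %, it runs from 1.57 to 2.38.

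**3. Equal but front-loaded risk.**

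- First-year hazard 3 %, then 0.25 % per year, contact 2024, whole years as in step 1: 5.5 % against 4.2 %, ratio 1.3.
- The remaining cases use contact at the start of 2024 with the cohorts meeting in mid-2016 (Ajust 7.5-15 years, TVT-A 3-7.5 years).
- First-year hazard 3 % then 1 %, 5 % then 0.5 %, 5 % then 0.2 %: ratios 1.77, 1.40 and 1.20.
- Weibull risk, 1 - exp(-λ·t^k), with λ set so that 5 % have the event by year 5: ratios 1.74, 1.45 and 1.21 for k = 0.75, 0.5 and 0.25. Constant risk (k = 1) gives 2.08 in the same layout.

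**4. With a common time scale.** Cumulative incidence at the same year after surgery is 1 - exp(-h·t) at one t for both slings, so the ratio at equal risk is 1.0.

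**5. The comparison wording.** The secondary outcomes speak of differences and the follow-up paragraph of both groups, while the statistics section excludes group comparisons for this part. Both cannot stand as written.

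**The case against.** The strongest reply has four parts.

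*The protocol does not prescribe a crude percentage.* This stands. A reader might infer that each event outcome will be reported as one ever/never percentage, because that is how satisfaction is defined. For these events, however, the denominator is unstated, and an analysis plan not shown could use time-to-event methods. What a later plan cannot supply is event dates that were never collected. The protocol mentions none, and the long-term questionnaire is described as a single contact.

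*No comparison is planned.* If the statistics section governs, there is no formal Ajust versus TVT-A result. That weakens the comparative harm but does not remove the point: the wording about differences says otherwise, and a percentage over mixed observation times still has no stated period.

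*Twofold is near the upper end.* This stands for total complications, which cover all types and so include perioperative and early events. A reader might infer that Ajust would show twice the TVT-A rate at equal yearly risk. That requires the risk to be constant as well as equal.

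*Not everything in the quoted sentence accumulates.* This also stands. Urgency is scored at follow-up, and in TVT-A women exposure is also looked for at the physical examination. These are findings on the day.

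**Conclusion.** The point holds in a conditional form. The protocol ties length of observation almost wholly to sling and gives the event-type outcomes no time since surgery. If they are reported as percentages of women, equal true risk would appear as an Ajust excess of about 1.9-2.1 times under a constant low yearly risk, and about 1.2-1.8 times if risk is front-loaded. All scenarios examined go in the same direction. The size rests on assumed yearly risks, an assumed contact year and evenly spread operations.

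Two stronger conclusions are not supported. One is that a pooled figure, 744/1062 = 70 % Ajust, will overstate risk. At 0.5 % per year the pooled share would be 4.8 %, against a 4-year risk of 2.0 %, but the protocol announces no pooled figure and those are different quantities. The other is that the two percentages must never be shown together. Showing follow-up length beside them is enough to prevent misreading.

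These are secondary outcomes, but they carry the study's safety message, and event dates are most easily secured before the questionnaire goes out. The change should be made.

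**What to change.** 1. Reconcile the wording about differences with the statement that Part 2 makes no group comparisons.
2. Record the date, or at least the year, of re-operation, whole or partial sling removal, and treated tape exposure, by one added questionnaire item or a record look-up.
3. For these events, report cumulative incidence from the index operation, censored at the follow-up contact, separately by sling. Give it at a horizon both groups reach, and at later years only while women remain under observation. Four years is the protocol's stated minimum; check it against actual contact dates, since contact in 2023 would leave women operated in 2020 at about three years.
4. Report complications without a date by band of years since surgery, and show the distribution of follow-up length beside any crude percentage.
5. Keep exposure found at examination and urgency scored at follow-up as statuses on the day.

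The cost is some outcome wording, one item or look-up, and slightly more analysis, with no change to recruitment or visits. Some self-reported dates will be approximate, and the common-horizon figure leaves out later events, which is why the later-year estimates should accompany it.

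### The pain outcome behind Part 3's 'development of chronic pelvic pain' sets no condition on pain before surgery, so prior pain can be counted as new

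*Protocol*

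**What the plan says.** Part 3 (PhD-project, Part 3, Primary outcomes) looks for associations between sling position, tension or anchoring and "subjective and objective cure rate, complication rates and especially the development of chronic pelvic pain". Its null hypothesis likewise covers "subjective and objective outcomes including complications such as chronic pain development". Part 3 gives no pain definition of its own. Its secondary outcomes refer to Part 2 for chronic pelvic pain.

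Part 2 (1) Long-term subjective outcomes, Secondary outcomes) does not define chronic pelvic pain. It defines prolonged pain through two alternatives:

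- first limb: "Differences in prolonged pain defined as postoperative pain more than 3 months after surgery in the NFIR questionnaire"
- second limb: "or having had treatment for pain caused by the surgery, e.g removal of the sling or part of the sling"

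Women whose pain is still ongoing also complete a new, non-validated pain form (reference 40, dated 2022).

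In the same list, de novo urgency incontinence is a follow-up score of at least 4, counted only "in women who had no urgency incontinence symptoms before surgery (preoperative urgency urinary incontinence score = 0").

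The Background says that registry data are collected before surgery. It does not say whether they include pain.

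**The concern.** Development means new onset, but the first limb fixes only when the pain is present, not when it began. A woman with pelvic pain before the operation and the same pain a year later meets the limb as written. The authors apply a baseline condition to urgency and leave it out for the complication that Part 3 stresses most.

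Two results are at stake. In Part 2 the prolonged-pain rate is presented as a complication of the sling, and prior pain would raise it. In Part 3, pain that preceded the sling and is unrelated to its position adds a common background to both position groups. A real link between position and new pain becomes harder to see.

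This differs from a choice of analysis model, which an analysis plan could settle later. If prior pain is neither on record nor asked, no later analysis can recover it.

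**Working it through.** **The plan's own figure.** The only sample size is 107 women for the ultrasound part (Statistics, power and sample size). Its inputs are 85 % versus 55 % subjectively cured, a 1:4 ratio, α 0.05 and power 80 %. With the arcsine formula, two-sided:

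- h = 2·asin√0.85 − 2·asin√0.55 = 0.675
- smaller group = (1.960 + 0.842)² × (1 + 1/4) / h² = 21.5
- total = 5 × 21.52 = 107.6

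This agrees with the stated 107. The calculation concerns cure, so the pain definition does not change it.

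**The definitions side by side.**

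| Outcome | Condition at follow-up | Condition before surgery | Attribution to surgery |
|---|---|---|---|
| De novo urgency | score ≥ 4 | score = 0 | none |
| Prolonged pain, first limb | pain more than 3 months after surgery | none stated | none stated |
| Prolonged pain, second limb | treated pain | none stated | stated |

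The two pain limbs are joined by *or*, so the attribution in the second does not restrict the first.

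**Illustration of size (all pain rates assumed).** Let b be the share of women with pain before surgery and d the risk of new pain, independent of each other. If all prior pain is reported as postoperative:

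counted pain = 1 − (1 − b)(1 − d)

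*Part 2.* Take b from 2 % to 10 % and d from 2 % to 4 %.

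- b = 2 %, d = 4 %: 1 − 0.98 × 0.96 = 5.9 %; prior share 2/5.92 = 34 %
- b = 10 %, d = 2 %: 1 − 0.90 × 0.98 = 11.8 %; prior share 10/11.8 = 85 %

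*Part 3, ratio.* Take new pain of 3 % (optimal position) versus 12 % (non-optimal), a true ratio of 4.0.

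- b = 5 %: 1 − 0.95 × 0.97 = 7.85 % and 1 − 0.95 × 0.88 = 16.4 %; ratio 2.1
- b = 10 %: 1 − 0.90 × 0.97 = 12.7 % and 1 − 0.90 × 0.88 = 20.8 %; ratio 1.6

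*Part 3, power.* The risk difference shrinks only by the factor (1 − b), but the variance grows. Take new pain of 5 % versus 20 % and the expected 50 % of 318 = 159 women at 1:4. A two-sided normal-approximation test at 0.05 gives:

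| b | Optimal | Non-optimal | Difference | Power |
|---|---|---|---|---|
| 0 % | 5.0 % | 20.0 % | 15.0 % | 0.73 |
| 5 % | 9.8 % | 24.0 % | 14.2 % | 0.57 |
| 10 % | 14.5 % | 28.0 % | 13.5 % | 0.45 |
| 20 % | 24.0 % | 36.0 % | 12.0 % | 0.29 |
| 30 % | 33.5 % | 44.0 % | 10.5 % | 0.20 |

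*Partial misreporting.* If only a fraction f of prior pain is reported as postoperative, b is replaced by f·b. With b = 10 % and f = 0.5 the b = 5 % results apply. With f = 0, for example because the questionnaire item already asks about onset, the bias vanishes.

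**The case against.** A reader might infer that prior pain **is** being counted as new. The protocol does not show that. The registry's pain item is not reproduced, and the word postoperative, in a list of complications, may reflect an item that carries onset or attribution. The reference 40 form is not reproduced either and may ask when the pain began. The preoperative registry record may hold pain. This objection stands, and it limits the point to what the written rule permits.

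A reader might also take the 2022 date of the new form as proof that no baseline exists. The form is indeed later than every operation (up to 2020, or 2021 if the period is extended), so it cannot supply a preoperative value. But it is a supplement for women with ongoing pain and is not the outcome measure. Its date says nothing about other sources.

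The importance can be contested too. Pain is one of several secondary outcomes in Part 2, which makes no group comparison in its first stage. Part 3's aim and secondary outcome speak of chronic pelvic pain without the word development. That inconsistency is real, but the primary outcome and the null hypothesis both use the stronger word.

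Finally, an analysis plan that is not shown may restrict or adjust for baseline pain. It can do so only if the information is collected.

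**Conclusion.** The point holds as a gap in the outcome definition. Applied literally, the rule cannot separate pain present before the sling from pain that began after it, and Part 3 rests a new-onset outcome on it. Prior pain can be counted as developed; whether it is, and how often, cannot be read from the protocol.

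The shares of 34 % to 85 %, the diluted ratios and the power losses are not estimates. They rest on assumed pain rates, on all prior pain being reported as postoperative, and on prior pain being independent of new pain and of sling position. They show the worst case under those rates, and the true effect could be close to nil. If prior pain were related to position, the direction of the bias in Part 3 would no longer be certain. Nor can one infer that the study is too small for its stated purpose: the 107 women are calculated for subjective cure.

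The matter should be settled before the questionnaires go out.

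**What to change.** 1. Establish whether the preoperative registry record, the registry's pain item or the reference 40 form captures prior pain or its onset. State the answer in the protocol and use that source if it exists.
2. If none does, add two items before dispatch: whether this pain was present before the sling operation, and when it started.
3. For Part 3, define development as pain with onset after the index operation in women without that pain before it, parallel to the urgency rule. Say at the same place how chronic pelvic pain relates to prolonged pain, since only the latter is defined.
4. Report all pain at follow-up separately as prevalence, including prior pain that worsened. Otherwise the restriction in step 3 would lose pain aggravated by the sling.
5. Name recall as a limitation. It spans 4 to 14 years and may differ by outcome, since women with poor results may be more inclined to date their pain to the operation.
6. If prior status cannot be obtained, reword the Part 3 primary outcome and null hypothesis to the presence of prolonged pain at follow-up.

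The cost is at most two questionnaire items and some wording. The number of new-pain cases will be smaller than the total pain count, and where it rests on recall it will be imperfect. The sample size needs no change.

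### Part 3 images the sling once, years after surgery and together with the outcomes, so it can describe position at follow-up but cannot establish where a sling is best placed

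*Protocol*

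**What the plan says.** The protocol heads Part 3 with "Study design: Prospective observational study". Its population is "318 women having had surgery with the intermediate sling TVT-A at AHUS between 2016 and 2020".

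The exposure is given as "Position, tension (shape) and anchoring of the sling, and measuring sling position in relation to well-defined anatomical markers". It is obtained at the long-term visit: "Women who consent to study participation and attend the physical follow-up will undergo a clinical examination that includes a transperineal ultrasound (TPUS) examination". The protocol describes no scan at surgery or soon after it.

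The outcomes are defined in Part 2:

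- **Objective cure** is assessed at the physical follow-up, where the women "will undergo a clinical examination including assessment of objective cure".
- **Subjective cure** comes from the questionnaire sent with the study invitation.
- **Prolonged pain** is "postoperative pain more than 3 months after surgery in the NFIR questionnaire or having had treatment for pain caused by the surgery". Removal of all or part of the sling is given as an example of such treatment.
- **Re-operation** is a separate secondary outcome.

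The formal aim, null hypothesis and endpoints of Part 3 are worded as associations. The Background, the Part 3 introduction and the section on potential impact also speak of finding an optimal zone for sling placement. The Background says "How the positioning of intermediate slings under the urethra may affect long-term success rates and adverse events is largely unknown". The Part 3 sample size section reasons from placement too: "As there is little scientific published data on how sling placement affect subjective and objective outcomes of sling surgeries".

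**The concern.** A statement about where a sling should be placed needs a measure of where it was placed, taken before the outcome. Part 3 has only the position seen years later. That position is measured relative to anatomical markers, and it can differ from the original one because the pelvic floor has changed, prolapse has developed, or the sling has been cut, revised or partly removed. Each of these may also bear on continence or pain. Removal goes further: it counts towards the pain outcome and also alters or abolishes the exposure being scanned.

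An association between late position and outcome could therefore appear even if original placement made no difference. The protocol nowhere says that the scanned position may differ from the position at surgery. The risk is that a valid description of women at follow-up is published as a placement zone. Reading the images masked to outcome would not help, because the problem is the order of events and not the reading.

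**Working it through.** **1. The plan's own figure.** The Part 3 sample size is 107, for cure of 85 % against 55 %, a group ratio of 1:4, α = 0.05 (taken as two-sided) and 80 % power. The arcsine formula reproduces it:

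- h = 2·arcsin√0.85 − 2·arcsin√0.55 = 0.675
- smaller group = (1.960 + 0.842)² × (1 + 1/4) / h² = 21.52
- total = 5 × 21.52 = 107.6

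The expected attendance of 50 % of 318 = 159 gives about 93 % power for the same difference. The sample size is not the problem here, and it cannot settle the order of events.

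**2. Timing.** The only evaluation year in the protocol is 2024, named as the earliest date for an optional group operated in 2021. Applied to the main group, it gives 2024 − 2020 = 4 years to 2024 − 2016 = 8 years. Scans in 2025 would give 5 to 9. The protocol itself states only 4 to 14 years, for both slings together.

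**3. Order of exposure and outcome.**

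| Item | When it is determined |
|---|---|
| Sling position, tension, anchoring | Ultrasound at the late physical follow-up |
| Objective cure | Same follow-up |
| Subjective cure | Questionnaire sent with the invitation |
| Prolonged pain | From 3 months after surgery, so possibly years before the scan |
| Re-operation, removal of all or part of the sling | Any time after surgery, so possibly before the scan |

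No outcome is shown to follow the measured exposure. Cure is measured at about the same time, and the others may come before.

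**4. Illustration A: a later common cause.** The inputs are assumed, except that they keep the protocol's 80:20 split and borrow its 85 % and 55 % cure rates. Placement has no effect. A later pelvic-floor change occurs in 20 % of women, raises non-optimal position from 15 % to 40 %, and lowers cure from 85 % to 55 %.

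- Non-optimal at scan: 0.8 × 0.15 + 0.2 × 0.40 = 0.12 + 0.08 = 0.20
- Cure if non-optimal: (0.12 × 0.85 + 0.08 × 0.55) / 0.20 = 0.730
- Cure if optimal: (0.68 × 0.85 + 0.12 × 0.55) / 0.80 = 0.805
- Apparent difference: 0.805 − 0.730 = 0.075, or 7.5 points; 7.5 / 30 = one quarter of the planned difference

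**5. Illustration B: failures seen outside the zone.** Again assumed. Cure is 0.8 × 0.85 + 0.2 × 0.55 = 79 % whatever the placement, and 80 % of slings were placed inside the zone. A share m of the failures placed inside is seen outside at the late scan.

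- Inside at scan: 0.8 × (1 − 0.21m), of whom 0.8 × 0.79 = 0.632 are cured
- Outside at scan: the remainder, of whom 0.2 × 0.79 = 0.158 are cured

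| m | Cure inside | Cure outside | Apparent difference |
|---|---|---|---|
| 10 % | 80.7 % | 72.9 % | 8 points |
| 20 % | 82.5 % | 67.6 % | 15 points |
| 30 % | 84.3 % | 63.1 % | 21 points |
| 40 % | 86.2 % | 59.1 % | 27 points |

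B uses a different mechanism from A, so it does not confirm the 7.5 points. It shows how far the result depends on assumptions that these data cannot test.

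**The case against.** The strongest reply is that the formal plan claims only association. The aim, null hypothesis and endpoints all say so, and one late scan can estimate an association. The most concrete use named for the zone is also postoperative: evaluating women who need repeat surgery, have failed treatment or have severe long-term complications. Both points stand. A reader might infer that Part 3 is invalid or promises guidance for the operating theatre. The documents support neither reading. The nearest text is a general hope of developing treatment techniques further.

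The word prospective is also defensible in a narrow sense, since the women are invited, consent and provide newly collected data. That is fair, but it does not put exposure before outcome.

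A reader might infer that every outcome precedes the scan. That is too strong. It can be true of pain, re-operation and earlier failure, whereas cure, on which the sample size rests, is current status measured around the scan.

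The 7.5 points might be taken as an estimate of bias. They are not, because the inputs have no source in the protocol. With 159 women split about 32:127, such a difference would reach significance only about 14 % of the time: standard error √(0.73 × 0.27/32 + 0.805 × 0.195/127) = 0.086, and 0.075/0.086 = 0.87 against a critical value of 1.96.

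Finally, it is tempting to restrict the main analysis to women whose sling was never cut, revised or removed. The documents speak against this. Removal is part of the pain definition and re-operation is an outcome, so the restriction would select on the outcome and drop severe pain cases, which are the protocol's stated focus. Restricting to women without prolapse has a similar flaw, since development of prolapse is itself a secondary outcome.

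**Conclusion.** The point holds in a limited form. For exposure and outcome, Part 3 is cross-sectional within a historical surgical cohort. It can answer its literal question, whether sling position, tension or anchoring at long-term follow-up is associated with outcome. It cannot support a zone read as placement at surgery, or an effect of placement on cure or on the development of pain.

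This conclusion rests on the absence of any earlier scan in the protocol, on the timing of the outcomes, and on removal being both an outcome and a change to the exposure. It does not depend on the illustrations, which give 7.5 points in one assumed scenario and 8 to 27 points in another, against a planned 30. The interval of 4 to 8 years assumes scans in 2024.

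A statistical analysis plan could specify how revised slings are handled. It could not supply an early scan, and the design label and the aim are fixed in the protocol. The change should be made because it governs what the study may conclude, but it does not affect the conduct or size of the study.

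**What to change.** 1. Describe the position-outcome comparison in Part 3 as cross-sectional, within a cohort of women operated in 2016 to 2020.
2. Replace the placement-zone wording throughout by sling position at long-term follow-up associated with outcome. State that this position may differ from the one at surgery.
3. Limit the stated conclusion to assessing women at follow-up.
4. Keep all women with a measurable sling in the main analysis. Count and report separately those whose sling was cut, revised or removed.
5. Add a sensitivity analysis in women with an unrevised sling for subjective and objective cure only. Do not apply this restriction to pain, complication or re-operation outcomes.
6. An analysis by POP-Q status is optional. If done, label it exploratory, because prolapse is itself a post-surgical outcome.

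The cost is wording, a count and one further analysis, using re-operation and complication data already planned. No visit is added and the sample size does not change. The downside is a more modest claim. The size of the sensitivity analysis cannot be given in advance, because the protocol states no revision rate.
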